This raises the question whether there are simple analyses that throw more appropriate light on the psychometrics of using the questionnaires to measure individual change than do the conventional explorations of psychometric quality of multi-item questionnaire measures for cross-sectional comparisons between people. This will be explored (details in the PPDAC "A" section: analyses, below).

- iii. As most existing data on the well-being and mental health problems of this age group are from student samples, a primary focus will be on differences between a student and a non-student sample both at baseline and subsequently through the year.
- iv. How much do scores on the dependent measures (CORE-OM, EQ-5D-3L and EQ-VAS, see registration) vary across the seven time points and is there evidence that the level of variation varies across the sample, i.e. that temporal stability is not a consistent parameter but show strong individual differences? Analyses of the CORE-OM will consider the non-risk and risk scores only (but see "supplementary analyses").
- v. Does baseline group, student vs. non-student, appear to relate to the dependent variables? Do other demographic predictors relate to the dependent variables? Recognising that "the dependent variables" will have temporal variation this will be divided into two sets of analyses:
 - 1. Using baseline scores only
 - 2. Analysing the full change data (more details below):
 - a. Testing for difference in any systematic linear trend over the seven time points.
 - b. Against within-participant SD of the scores.
 - c. Against highest and lowest within-participant difference from baseline.
- vi. What levels of and changes in stressors/life events (LE) do participants report on the novel "What's going on?" (WGO) measure?
- vii. Is there evidence of systematic relationship between stress and dependent variable scores within-participant over time?
- viii. Given the inevitably non-random nature of the sampling creating the dataset this will be compared with the most recently available census data

from Quito for this age group to see how much the sample differs from the census data where comparable variables are present in the census data.

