This is a hybrid qualitative and quantitative measure previously only been used in a study of adolescent school students in the UK (personal communication) hence this be only the second use of this measure. If person power can be found the events described by participants will be analysed using simple thematic analysis and associations of major themes with group, other demographics and dependent variable scores will be reported.
- P (Plan): *already spelled out in registration*
- D (Data): *ditto*

- A (Analyses): These will be divided into two tranches (see also [Communication](#), below): analyses of baseline data and analyses of change when all data collection has been completed.

All analyses will be conducted using R (R Core Team, 2020) and platform, R version and all non-base packages used will be reported either in publications or in publicly accessible supplementary material.

- **Baseline analyses**

- Demographic characteristics and baseline WGO and dependent variables scores will be reported. Primary presentations will be graphical with plots describing the diversity in the data (violin and scatter plots). Where available referential Ecuadorean data exist, sample statistics will be compared with referential data with CIs indicating precision of estimation. CIs for binary proportions will use Wilson's method and bootstrap CIs will be used for other variables, 95% intervals for CIs will be used throughout. Findings will be discussed with reference to likely systematic non-participation bias revealed in the comparisons. As well as the comparisons with other Ecuadorean data reported in the paper, CIs will allow readers to compare findings with data from other samples or populations of interest/concern to them taking into account likely imprecision of estimation in the study.
 - Where associations between baseline variables, including group, are statistically significant at $p < .01$ the interactions between these predictors and the dependent variables will be reported to throw light on the likely systematic associations between variables and the potential to confound one primary focus of interest: the differences between the two groups. The alpha value of .01 has been chosen *a priori* to select moderately strong associations and provide some control of the inevitably elevated rate of "false positives" above .05 that arises from multiple tests if an alpha of .05 is used.

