Some participants will probably change group during the year though these will probably be less numerous than "students-who-also-hold-jobs". Due to the timing of the data collection, students are probably more likely to terminate their courses during the year than are non-students to start a degree. Here again, sensitivity analyses will be conducted recomputing the analyses (a) omitting participants who change group at any point in the year and (b) omitting only those changing group whose change comes less than half way through the year and (c) reallocating those who change group to the group they fall in for more than half the year. However, the expectation is that the numbers changing group will be small and the impacts on the ITT findings small or negligible.

Recognising that these dependent variables have temporal variation and this variation is likely to be complexly patterned across the entire sample, the following analyses will be reported for the ITT baseline group comparison and the sensitivity analyses noted above.

- Group difference against mean scores across all non-missing scores from all seven occasions. This extends the analyses of baseline group differences and entirely ignores change over time.
- Group difference in linear trend over the time points using multi-level modelling (MLM). This allows a trend to be fitted both as a fixed effect whose interaction with predictors can be tested, i.e. assuming a single within-group population mean, and then also allowing a free effect, i.e. allowing that linear trend against time may vary between individuals. The MLM provides an individual (free) linear slope if scores at least two time points exist. However, sensitivity checks on effects of missingness will be added by restricting to sequentially larger numbers of time points.
- Group differences in within-participant SD of the scores (wpSD).
- Group differences in within-participant score difference from baseline (wpMaxChange).
- Group differences in within-participant score range (wpScoreRange).
- Do other demographic predictors relate to the dependent variables? Same methods as for group differences.

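### The plan raises confounding of the student versus non-student difference, but its p < .01 screen followed by interactions does not reliably identify confounders and yields no adjusted group difference.

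*SAP*

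**What the plan says.** In the SAP's list of specific questions (PPDAC approach), question iii states that "a primary focus will be on differences between a student and a non-student sample both at baseline and subsequently through the year".

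Under Baseline analyses, the plan tests associations between baseline variables, group among them, at p < .01. Where one is significant, "the interactions between these predictors and the dependent variables will be reported to throw light on the likely systematic associations between variables" and on "the potential to confound one primary focus of interest: the differences between the two groups". The threshold is said to have been chosen in advance "to select moderately strong associations" and to give some control of false positives over many tests. The next bullet concedes, with hindsight, that other ways of exploring these complexities exist, but it fixes none.

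Under Change analyses, the group comparisons cover the mean score over all occasions, the linear trend in a multi-level model (MLM), wpSD, wpMaxChange and wpScoreRange. No covariate is named for any of them. Other demographic predictors are a separate question, answered by "Same methods as for group differences". The sensitivity analyses deal with how group is defined (students with jobs, participants who change group) and with missing occasions.

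**The concern.** The plan identifies a threat to one of its main contrasts and then fixes a procedure that does not measure it. Three gaps follow.

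- An interaction asks whether the group difference varies with a covariate. A covariate can confound the group difference fully with no interaction at all.
- A significance screen on associations between baseline variables responds to sample size as well as to strength of association. Its stated trigger does not consider how strongly the covariate relates to the outcome, and confounding depends on both links.
- Flagging a covariate leads to no estimate of the group difference with that covariate held constant.

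If the groups differ in background variables that also relate to distress, part of that difference could be read as a difference between students and non-students, both at baseline and over the year.

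**Working it through.** **Figures in the plan.** The only number is the .01 threshold. The SAP states no group size, imbalance, slope or power for this comparison, so there is no figure to reproduce. Everything below is illustrative, with assumed inputs and a two-sided test (the SAP does not state sidedness).

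**Step 1. What effect size does p < .01 select?** For a correlation, the critical value is |r| = t / √(N − 2 + t²), with t the two-sided .01 point on N − 2 degrees of freedom.

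| Total N (assumed) | 100 | 200 | 300 | 600 | 1000 |
|---|---|---|---|---|---|
| Smallest significant \|r\| | .26 | .18 | .15 | .11 | .08 |

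The selected strength changes about threefold over this range, so the threshold alone does not define a moderately strong association.

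**Step 2. How often is an imbalance flagged?** For a covariate whose group means differ by d SD, with n per group, the standard error is √(2/n). The screen flags an observed difference above 2.576 × √(2/n), with probability about Φ(d/√(2/n) − 2.576). For n = 200 and d = 0.3: √(2/200) = 0.10, and Φ(3.0 − 2.576) = Φ(0.424) = 66%.

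| n per group (assumed) | 100 | 200 | 300 | 500 |
|---|---|---|---|---|
| Screen threshold, SD | 0.36 | 0.26 | 0.21 | 0.16 |
| d = 0.2 flagged | 12% | 28% | 45% | 72% |
| d = 0.3 flagged | 33% | 66% | 86% | 98% |

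Large imbalances are usually caught: in simulation, d = 0.5 was flagged in 81% of runs at 100 per group and 99% at 200.

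**Step 3. What does one confounder do to the unadjusted difference?** The shift is d × b, where b is the standardised slope of outcome on covariate.

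- d = 0.3, b = 0.3: 0.3 × 0.3 = 0.09 SD. With 200 per group the standard error of the difference is about 0.10, so the shift is about 0.9 standard errors. A 5% test of a true null then rejects in about Φ(0.9 − 1.96) + Φ(−0.9 − 1.96) = 0.145 + 0.002, or 15%.
- d = 0.5, b = 0.3: 0.5 × 0.3 = 0.15 SD.
- An imbalance exactly at the screen threshold gives a shift of b × 2.576 standard errors at any n: 0.77 standard errors for b = 0.3 and 1.29 for b = 0.5.

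**Step 4. Does the interaction reveal confounding?** This was simulated with no true group difference, no interaction, b = 0.5 and 3,000 runs per setting. Results for 200 per group:

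| d | Unadjusted difference, SD | Unadjusted 5% test rejects | Adjusted difference, SD | Adjusted test rejects | Interaction test rejects |
|---|---|---|---|---|---|
| 0.2 | 0.10 | 17% | 0.00 | 5.5% | 5.2% |
| 0.3 | 0.15 | 33% | 0.00 | 5.1% | 6.1% |
| 0.5 | 0.25 | 71% | 0.00 | 5.1% | 5.2% |

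Over all settings (100, 200 and 300 per group) the interaction test rejected in about 4% to 6% of runs, its null rate. It carries no signal of confounding when there is no effect modification. Adjustment removes the shift here because the only confounder is measured and correctly modelled.

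**The case against.** **The plan does not promise to remove confounding.** It says that the interactions throw light on it, and it presents the study as exploratory, descriptive and estimation-based. Question iii is motivated by the predominance of student samples in existing data, so the unadjusted difference is a legitimate target. This stands, and it is why the unadjusted estimate should stay. It does not rescue the procedure: having raised confounding, the plan chose a tool that does not inform on it, and a shift from confounding affects the estimate and its CI as much as a p value.

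**The wording is loose.** A model with group, covariate and their product would normally include the covariate's main effect, and the MLM item speaks of interactions with predictors in the plural. That is fair. But the SAP does not say that such a model will be fitted, or that a group difference will be reported from it.

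**The .01 level also serves multiplicity.** That part of the rationale holds. With independent tests, the chance of at least one false flag, 1 − 0.99^k, is 4.9% for 5 tests, 9.6% for 10 and 18% for 20. It does not support the claim about strength of association.

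**Stronger readings that the document does not support.** A reader might infer:

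- that the screen misses confounders altogether. Large imbalances usually are flagged.
- that demographics will be analysed one at a time. The SAP says only that the methods are the same as for group.
- that biases accumulate over covariates. They carry signs, may cancel, and overlap when covariates are correlated.
- that the reported difference is known to be biased by a given amount. No input for that is in the document.

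**Conclusion.** The point holds as a gap between a stated worry and the analysis meant to address it. The rule does not reliably identify confounders, and no covariate-adjusted group difference is specified at baseline or over the year. The phrase about moderately strong associations is not true of a p value threshold unless N is fixed.

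The possible size is modest for a single covariate: about 0.09 SD for an imbalance of 0.3 SD with slope 0.3, and 0.15 SD for 0.5 SD with slope 0.3. These figures rest on assumed group sizes, imbalances and slopes. They show what could happen, not what did.

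**What to change.** For the change analyses, which according to the SAP's history section had not been inspected at v2.2, pre-specify the following:

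1. Report each group difference (mean level, MLM trend, wpSD, wpMaxChange, wpScoreRange) twice with 95% CIs: unadjusted, as the descriptive quantity, and adjusted for a fixed set of baseline demographics already collected.
2. Choose that set on subject-matter grounds and enter it whatever the p values. Leave out variables that define or follow from group, such as employment; the planned analyses of students with jobs already deal with that. For the MLM trend, include covariate-by-time terms, since covariate main effects alone adjust only the level.
3. Report the same pair for baseline scores, marked as post hoc because the baseline analyses are done and the paper was submitted.
4. Keep interactions as a separate look at effect modification.
5. Delete the phrase about moderately strong associations, or define it by an effect size.

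The cost is an amendment to the SAP, of a kind its own history section allows for, and additional model runs on data already collected. The downside is two estimates per comparison to explain. The adjusted one will still be open to confounders that were not measured.

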- One key focus is on how much scores on the three dependent measures, CORE-OM, EQ-5D-3L and EQ-VAS vary across the seven time points and particularly the question of whether that variation over time appears to vary systematically across individuals, i.e. that the within individual variance is not compatible with a null model of a shared population parameter showing only random individual differences? As is common in such studies (e.g., Cooper & McConville, 1990; McConville & Cooper, 1996; Murray et al., 2002) the within-participant standard deviation of the scores, "wpSD" across the seven assessment points will be reported and its distribution (histogram with individual points) plotted. The Levene test, an extension of the Bartlett test, will be used to test for heteroscedasticity, i.e. that null hypothesis of that this variance within group (i.e. here participants) is likely to have arisen by sampling vagaries from a shared population value. The Levene is said to give results in which the null hypothesis is rejected at the conventional alpha level of 0.05 more robustly for non-Gaussian distributions than does the Bartlett test.

The wpSD is useful as it is a sensible statistic aggregating change across all occasions. However, in terms of possible implications for liability to gain from help, the aggregation across all measure completions risk hiding particularly high peak scores so two other within-participant change summary indices will be computed:

- Signed maximum change from baseline score ("wpMaxChange").
- Absolute maximum difference between any two completed scores ("wpScoreRange").

These don't allow a formal test for homogeneity of change across participants but they do throw light on possible "spike" and "trough" changes.

All three within-participant summary indices will be positively correlated with each other and this correlation will be reported and the findings carefully reported as correlated but addressing issues whose differences are of interest.

- As noted, the baseline psychometric analyses, while useful guides to the internal reliability of the multi-item measures for comparisons across individuals at a single measurement occasion. However, the cross-sectional,

conventional test theory underlying that use of the internal reliability does not necessarily fit measurement of change within-participants. This will be explored as follows.

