- That still looks for some shared change across individuals. Dropping that measurement expectation entirely, but transferring CTT to within-participant change allows computation of the alpha for change within-participant. The parametric 95% confidence interval for an observed alpha of .6 from $n = 7$ (i.e. all seven occasions) for 28 items (the CORE-OM-NR) is from 0.0 to .92, i.e. reaching a point at which a model of no reliability of within-participant change is looking implausible. We will report within-participant Cronbach alpha values for all participants with full item data from all seven occasions for the CORE-OM-NR score and also, separately, for those with fewer occasions. Where the parametric lower confidence interval exceeds zero the first principal components of the within-participant PCA will be inspected and it is expected that these will be markedly different for different participants with these high personal change Cronbach alpha values, illustrating that within-participant change on a measure like the CORE-OM can be reliable be markedly different in structure between individuals. This can also be done for all 34 items making up the full CORE-OM. For the shorter scales/scores such as the EQ-5D-3L or the domain scores of the CORE-OM the number of items are not sufficient to give any reasonable power to find internal reliability with only seven measurement occasions and this model will not be explored for the shorter scales/scores.
- Does baseline group, student vs. non-student, appear to relate to change on the dependent variables? All change scores and distributions will be plotted allowing both individual values and central location statistics with CIs to be seen.
All analyses will be firstly "intention to treat" (ITT), i.e. by baseline group.

However, many students will also hold jobs. How much this relates to scores on dependent variables will be explored by analysing with these "students-who-also-hold-jobs" as a group and by reclassifying them into the non-student group. These additional explorations will explore the sensitivity of any relationships to baseline group to these real world complexities.

It seems plausible that these "students-who-also-hold-jobs" are sufficiently different from either the students without any outside course employment or from the young people with jobs and no university study that this issue may need to be considered alongside the simple ITT analyses.

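### On bounded scores massed near one end, wpSD depends on the person's mean, so the raw-score variance test and the wpSD comparisons can reflect level rather than stability

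*SAP*

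**What the plan says.** Specific question iv (SAP, PPDAC approach, P) asks how much the dependent scores vary over the seven time points and whether temporal stability differs strongly between people. For this measure it says "Analyses of the CORE-OM will consider the non-risk and risk scores only". The scores concerned are therefore CORE-OM non-risk, CORE-OM risk, EQ-5D-3L and EQ-VAS.

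Under A (Analyses), Change analyses, this becomes a key focus, worded as whether "the within individual variance is not compatible with a null model of a shared population parameter showing only random individual differences". The wpSD "across the seven assessment points will be reported and its distribution (histogram with individual points) plotted". The test is then named: "The Levene test, an extension of the Bartlett test, will be used to test for heteroscedasticity", with each participant treated as a group. It is preferred to Bartlett's because "the null hypothesis is rejected at the conventional alpha level of 0.05 more robustly for non-Gaussian distributions".

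The later list of group analyses includes "Group differences in within-participant SD of the scores (wpSD"), and other demographic predictors are to be handled by the same methods. The group difference in mean score is a separate item in that list. The only dependence between indices that the SAP undertakes to report is among wpSD, wpMaxChange and wpScoreRange. Nowhere is wpSD related to the person's mean or adjusted for it.

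**The concern.** Someone whose true state lies at or beyond the end of a scale scores the same on every occasion, while someone of equal underlying instability in mid-scale moves. On such a score, equal raw-score variance is a false null for a reason that has nothing to do with individual differences in stability. Choosing a test that is robust to non-Gaussian shape does not help, because the variance itself depends on the mean.

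Two conclusions are at stake. Question iv could be answered yes on a score where the scale alone produces the rejection. A group or demographic factor associated with higher distress could also be reported as associated with greater instability, when the wpSD comparison is only repeating the difference in mean scores.

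**Working it through.** **Plan's own figure.** The SAP gives no sample size, effect size or power for wpSD, so there is nothing to reproduce.

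**Inputs from the SAP.** Seven occasions; Levene at alpha 0.05 with centring not stated; the non-risk score "for 28 items (the CORE-OM-NR"); and, for the full measure, "This can also be done for all 34 items making up the full CORE-OM". The risk score thus has 34 - 28 = 6 items.

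**Inputs assumed.** CORE-OM items scored 0-4, EQ-5D-3L as five three-level items, EQ-VAS 0-100 with high meaning good health, all mean levels, ICC 0.5 or 0.7, total N 200 or 600, and a group shift of 0.4 total latent SD.

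**Bound on wpSD.** For n scores between a and b with mean m, wpSD² ≤ [n/(n-1)] (m-a)(b-m). With n = 7, a = 0, b = 4:
- m = 0: wpSD = 0
- m = 0.3: wpSD ≤ √(7/6 × 0.3 × 3.7) = √1.295 = 1.14
- m = 2: wpSD ≤ √(7/6 × 2 × 2) = √4.667 = 2.16

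This is only a ceiling on wpSD. The simulation shows how far it matters in practice.

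**Simulation.** Every person had the same latent within-person SD, seven occasions and no attrition, and groups differed in level only (observed d 0.39-0.55). There were 200 replicates per cell. Ranges run over the two N and two ICC values. R² is from regressing wpSD on person mean and mean squared. The group test is Welch's; the adjusted version adds mean and mean squared.

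| Simulated score | Spearman, wpSD with mean | R² | Median-centred Levene rejects | wpSD group d | Group test rejects, raw | Adjusted |
|---|---|---|---|---|---|---|
| Unbounded control | 0.00 to 0.02 | 0.00-0.01 | 0% | about 0 | 4-7% | 6-7% |
| Risk-like, 6 items, mean 0.30, 53% at minimum | 0.95 to 0.96 | 0.82-0.83 | 100% | 0.38 to 0.42 | 82-99% | 4-5% |
| EQ-5D-like, 32% at minimum | 0.80 to 0.81 | 0.64-0.66 | 97-100% | 0.35 to 0.36 | 65-100% | 4-6% |
| 28 items, mean about 1.5 | 0.44 to 0.46 | 0.39-0.44 | 2-48% | 0.21 to 0.23 | 32-78% | 4-7% |
| 28 items, mean about 2.05 | -0.05 to -0.04 | 0.27-0.33 | 0-1% | about 0 | 3-7% | 3-7% |
| VAS, mean about 82 | -0.45 to -0.44 | 0.32-0.34 | 12-91% | -0.24 to -0.22 | 34-86% | 4-7% |
| VAS, mean about 73 | -0.16 to -0.15 | 0.07-0.09 | 0% | -0.10 to -0.08 | 10-20% | 3-5% |

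With 200 replicates the Monte Carlo standard error at 5% is √(0.05 × 0.95/200) = 1.5 percentage points, so adjusted rates of 3-7% are compatible with nominal.

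**Reading.** The control shows no dependence, which isolates the bounds as the cause. At mid-scale the relation is an arch, so R² is not zero, but a group shift produces no wpSD difference.

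**Sensitivity.** Runs with other assumed thresholds agree on the floored scores: Spearman 0.91-0.99, and 13-35% of people with wpSD exactly 0. For the 28-item score, median-centred Levene rejection ranged from 92-100% at a mean of about 1.2, through 2-48% at about 1.5, to 0% at mid-scale. Adjusted group rejection in one such set was 2-12%. With no level difference, the raw group test on the risk-like score stayed at 5%.

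**Centring.** On the unbounded control, mean-centred Levene rejected 42-48% (N = 200) and 78-84% (N = 600) under a true null. The table therefore uses the median-centred form. This is a separate weakness of the test, and it means a mean-centred rejection could not be credited to the bounds alone.

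**The case against.** A reader might infer that every wpSD result in this study merely restates level, that wpSD always rises with the mean, and that Levene's test must reject whatever the truth. The documents do not support that. The SAP gives no score ranges, means or floor shares, and does not say that most participants sit near the healthy end. The simulated effect varies sharply with those quantities: it dominates on floored scores, is moderate or absent for a 28-item score, is weak for a VAS averaging about 73, and has the opposite sign near a ceiling. A false group difference also requires a real difference in level.

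It can further be said that unequal variance of observed scores is a true description of those scores, and that the SAP's stance is exploratory and estimation-based, with tests serving only as pragmatic indications. The histogram of wpSD would show a spike at zero, baseline score distributions are to be reported, and mean-score differences stand in the same list. The SAP also makes a general promise to explore associations that complicate analyses.

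This limits the size of the point but does not remove it. Question iv is framed as temporal stability of persons, which goes beyond describing raw scores. A confidence interval around a level-driven wpSD difference misleads as much as a p value does. None of the planned displays puts wpSD against level.

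**Conclusion.** The point holds in a limited form. For scores massed near a bound, likely CORE-OM risk and EQ-5D-3L, rejecting equal raw-score variance is not by itself evidence that temporal stability differs between people. On those scores a pure level difference of about d 0.4-0.5 reappeared as a wpSD difference of d 0.35-0.42. For CORE-OM-NR and EQ-VAS the effect is smaller and may be absent, depending on where the scores sit. It vanishes where groups do not differ in level.

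The direction of the argument follows from the bounds. Every magnitude rests on the assumed item ranges, means, ICC, sample size and level shift. This is a cheap improvement that guards a stated key focus against a misleading answer.

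**What to change.** In the Change analyses, both where wpSD is introduced and in the list of group comparisons:

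- Plot wpSD against person mean for each score, and report the share of participants with wpSD of zero.
- Report group and demographic comparisons of wpSD twice: raw, and adjusted for person mean and its square.
- Base the answer to question iv on heterogeneity that remains given the mean, for example by comparison with a simulated null that keeps the scale bounds and a common latent variance. Do not rest it on the raw-score Levene test for floored scores.
- Do not rescale wpSD by the maximum SD possible at that mean. The ratio is 0/0 for anyone always at the floor, and on the floored scores it still gave false group differences in 14-43% of simulated samples.

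The cost is some SAP wording and a little R code, with no new data. The SAP's history section allows marked amendments and places v2.2 before any inspection of the change data. There is one downside: if instability truly rises with distress, adjustment removes part of a real effect. That is why both versions should be shown.
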